5.5.9 Prohibited treatment

Use of the treatments displayed in the table below are NOT allowed after the start of study drug until at least four weeks after the last administration of study drug.

Table 5-3 Prohibited treatment

Medication	Action to be taken
Other experimental therapies	Withdrawal may be required on a case-by-case basis
Other biologics	Withdrawal may be required on a case-by-case basis
Immune suppressive agents	Withdrawal may be required on a case-by-case basis
Any medication that, as judged by the Investigator, is the primary cause of dry mouth in the patients	Withdrawal may be required on a case-by-case basis
Live vaccination	Withdrawal immediately

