3.3 Rationale for dose/regimen, duration of treatment

No previous experience with an anti-CD40 blocking agent exists in human primary Sjögren's syndrome.

Corporate Confidential Information

Cohort 1 (subcutaneous

Corporate Confidential Information

The 2-week dosing interval at the start is meant to ensure full CD40 saturation on peripheral B cells as well as complete suppression of CD40-CD154 interaction in tissues after subcutaneous administration. By the end of the 12-week treatment period, clinically meaningful changes in the primary endpoint and in other key efficacy and biomarker readouts are expected to occur. Based on published results with a single cycle of rituximab, significant clinical responses in pSS patients can be detected as early as at week 5, with maximum effect shown at week 12 ([Meijer et al 2010](#)). During the additional 12-week open label extension period, further data regarding longer term efficacy and safety of CFZ533 will be collected.

Cohort 2 (intravenous -

The i.v. regimen is introduced to offer higher plasma exposures throughout the treatment period, in order to ensure complete and sustained CD40 pathway blockade in target tissues, in conditions where higher CD40 expression is likely. This regimen is supported by

Corporate Confidential Information

recently published data from ASKP1240.

Data from ASKP1240, a monoclonal antibody blocking CD40: A recent analysis of disclosed PK/efficacy data from Astellas' anti-CD40 antibody ASKP1240 in solid organ transplantation ([Harland et al 2015](#)) demonstrated that efficient target mediated antibody clearance in tissue, could result in loss of CD40 blockade and likely loss of efficacy, as a consequence of a significant increase of target expression in target tissues. The proposed intravenous regimen is aiming to saturate, throughout the entire treatment period, CD40 elimination pathways, in conditions where higher CD40 expression is likely.

Corporate
Confidential
Information

Cohort 3

Based on results from Cohorts 1 and 2 Corporate Confidential Information an efficient dosing regimen in patients with pSS may require a loading regimen (i.v. or s.c.), providing early full CD40 saturation and minimal target mediated disposition followed by a s.c. maintenance regimen.

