3.6.2 Potential risks associated with exposure to CFZ533 and their mitigation

Currently, limited data exists regarding the use of agents that block the CD40/CD154 pathway.

Corporate Confidential Information

The current IB (Section 6, Investigator Guidance) also provides detailed instructions regarding the risks and their mitigation.

Acute hypersensitivity

Hypersensitivity or infusion reactions can manifest with itching, flushing, headache, nausea/vomiting, hypotension, urticaria, bronchospasm, or angioedema. Corporate Confidential Information

Infections

Subjects treated with CFZ533 may be at an increased risk of infection. CD40 ligation is linked to the functional activity of antigen presentation, as well as T-cell priming, B-cell differentiation, antibody production and immune memory. Administration of CFZ533 is expected to result in general immunosuppression with a decreased capacity to mount a response to novel immunogens, including those of bacterial, viral, fungal and parasitic origin when full receptor occupancy has been achieved.

Although the ability to mount a primary immune response will be affected by CFZ533, the memory B-cell repertoire and immune recall response should remain intact and protective. In addition, subjects will have adequate preformed antibody to maintain protective humoral response for extended periods of time (months).

Corporate Confidential Information

Subjects enrolled in the current study will be monitored regularly and carefully for signs and symptoms which might indicate a severe infection. Subjects will be informed to contact the study physician if they present with signs and symptoms of an infection such as fever, nausea, myalgia, headache, arthralgia, chills, diarrhea, stiff neck, and malaise for further assessment and treatment if necessary.

Vaccination

Vaccination of subjects during treatment with CFZ533 and prior to clearance of the antibody is likely to result in therapeutic failure (i.e., non-protective antibody titers) due to the pharmacologic activity of the antibody. For subjects participating in this study, all vaccinations should be up to date based on local guidelines. Administration of live attenuated agents will be prohibited receiving CFZ533 treatment in the current study.

Immunogenicity

Corporate Confidential Information

Extrapolation of immunogenicity risks from healthy subjects to pSS patients is unknown and blood samples will be collected during this trial to assess this.

Thrombosis

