4.2 Exclusion criteria

Subjects fulfilling **any** of the following criteria are not eligible for inclusion in this study:

1. Secondary Sjögren's syndrome. Patients with laboratory or clinical signs of another connective tissue disease (e.g., systemic lupus erythematosus) may be eligible at the investigators discretion;
2. Use other investigational drugs at the time of enrollment, or is within five half-lives of using other investigational drugs or longer if required by local regulations, at the time of enrollment;
3. History of hypersensitivity to study drug or to drugs of similar chemical classes;

4. Patients having received the following treatments (within given timeframe before randomization):
- Oral or i.v. cyclophosphamide treatment within 6 months;
 - i.v. corticosteroid bolus with dose > 1 mg/kg within 3 months;
 - Rituximab within 12 months. For patient who received rituximab earlier, B cell count should be within normal range;
 - Belimumab within 6 month;
 - Any other biologic within 1 month or five times the half-life, whichever is longer;
 - Any other immunosuppressives (despite methotrexate, glucocorticoids, and hydroxychloroquine on stable doses as described in the inclusion criteria 8, 9, 10, 11) such as cyclosporine A or mycophenolate within 3 months;
- Corporate Confidential Information

11. Signs or symptoms of a clinically significant systemic viral, bacterial or fungal infection within 30 days of randomization;
12. Any condition, that would result in a significantly elevated risk for infections, as judged by the investigator, e.g.:
- Vaccinations as required based on local guidelines are not up to date;
 - Any form of clinically relevant immunodeficiency.
- Corporate Confidential Information

20. Pregnant or nursing (lactating) women, where pregnancy is defined as the state of a female after conception and until the termination of gestation, confirmed by a positive hCG laboratory test
21. Women of child-bearing potential, defined as all women physiologically capable of becoming pregnant, unless they are using highly effective methods of contraception during the study and for 12 weeks after the last study treatment. Highly effective contraception methods include:
 - Total abstinence (when this is in line with the preferred and usual lifestyle of the subject). Periodic abstinence (e.g., calendar, ovulation, symptothermal, post-ovulation methods) and withdrawal are not acceptable methods of contraception.

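### In Cohort 2 the four-week ban on live vaccines can end on Day 169, when the i.v. regimen is still meant to keep CD40 saturated

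*Protocol*

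**What the plan says.** Protocol 5.5.9 introduces Table 5-3 with one time window for all five rows: the treatments are "NOT allowed after the start of study drug until at least four weeks after the last administration of study drug". Live vaccination is one of the rows. It is the only one whose action is immediate withdrawal; the others are decided case by case.

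Section 3.3 gives the purpose of the Cohort 2 regimen. Higher exposure is sought "in order to ensure complete and sustained CD40 pathway blockade in target tissues", and "The proposed intravenous regimen is aiming to saturate, throughout the entire treatment period, CD40 elimination pathways". Section 3.1 runs the open-label period to Day 169.

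Section 3.6.2 makes three relevant statements:
- Under Infections, CFZ533 is "expected to result in general immunosuppression with a decreased capacity to mount a response to novel immunogens" once receptor occupancy is full.
- Under Vaccination, "Vaccination of subjects during treatment with CFZ533 and prior to clearance of the antibody is likely to result in therapeutic failure".
- Under Vaccination, "Administration of live attenuated agents will be prohibited receiving CFZ533 treatment in the current study". This names no period after the last dose.

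Two other washout rules appear in Section 4.2. Women of child-bearing potential are excluded "unless they are using highly effective methods of contraception during the study and for 12 weeks after the last study treatment". The washout for an earlier biologic is "Any other biologic within 1 month or five times the half-life, whichever is longer".

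**The concern.** A single four-week minimum serves rows with different risks. For a prohibited biologic or immunosuppressant, the issue is mainly overlapping treatment. For a live vaccine, what matters is whether the patient's immune response is still suppressed, and Section 3.6.2 links that to receptor occupancy and antibody clearance, not to a number of weeks. In Cohort 2 the four weeks equal the longest planned gap between doses, a gap across which the regimen is designed to hold CD40 saturated.

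The stake is patient safety. A patient given a live vaccine when the minimum expires could still have CD40 blocked and a reduced response to a new organism, and the vaccine might also fail to protect. The Week 13 efficacy comparison in fully dosed patients is not touched.

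**Working it through.** No sample-size or error-rate formula applies. The check is day arithmetic on nominal visit days, ignoring visit windows.

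**Inputs.** Dose days 1, 15, 29, 57, 85, 99, 113 and 141 (Section 3.1, Cohort 1; the Cohort 2 text keeps the same design apart from the regimen). Open-label period ends Day 169 and the end-of-study visit is Day 225 (Section 3.1). Follow-up lasts 8 weeks and ends 12 weeks after the last dose (Section 3.2). Minimum ban: 28 days after the last dose (Section 5.5.9).

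**Reproducing the plan's own figure.** 225 − 141 = 84 days = 12 weeks, and 225 − 169 = 56 days = 8 weeks. Both match Section 3.2, which confirms Day 141 as the last dose in both cohorts.

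**When the ban can end.** 141 + 28 = Day 169.

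**Dosing gaps.** 14, 14, 28, 28, 14, 14 and 28 days; then 169 − 141 = 28 days from the last dose to the end of the open-label period.

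**Does the saturation aim reach 28 days after a dose?** It does on either reading of the treatment period in Section 3.3.
- If it includes the open-label part, it ends on Day 169, which is 28 days after the Day 141 dose.
- If it means only the first 12 weeks, it ends on Day 85, and 85 − 57 = 28 days after the preceding dose. The open-label schedule repeats the first one 84 days later (57 + 84 = 141; 85 + 84 = 169), so Day 169 sits where Day 85 sat. This assumes equal doses in the two periods; the dose levels are redacted.

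**Side by side.** Section 3.3 intends saturation 28 days after a dose. Section 3.6.2 expects immunosuppression under full occupancy. Section 5.5.9 lets the live-vaccine ban end 28 days after the last dose.

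**Comparison with 12 weeks.** 141 + 84 = Day 225, so the two limits differ by 225 − 169 = 56 days (8 weeks). In Cohort 3 the last dose is Day 85: 85 + 28 = Day 113, and 85 + 84 = Day 169.

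**Half-life (assumed; none is given in the visible text).** Four weeks equals five half-lives only if the half-life is 28/5 = 5.6 days; for 12 weeks the figure is 84/5 = 16.8 days. For assumed half-lives of 7, 14 and 21 days, five half-lives are 35, 70 and 105 days, which is Day 176, Day 211 and Day 246 in Cohort 2. Section 3.2 describes target-mediated elimination that speeds up once saturation is incomplete, so a constant half-life is only a rough guide. The point does not rest on these values.

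**The case against.** The strongest reply is that the deciding material is out of view. Section 3.6.2 refers to the Investigator's Brochure for detailed mitigation, and parts of the dose rationale, the risk section and the exclusion criteria are redacted. A longer period may be set there. Four weeks is also a floor, and read with the clearance warning in Section 3.6.2 it could be taken as a minimum plus a caution. This stands in part: the finding concerns the visible protocol and makes no claim about actual receptor occupancy. But neither the floor nor the warning gives a site a later date or a clearance check, so a live vaccine on Day 169 would not be a deviation from the visible text.

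A second reply is that the 12-week periods serve other purposes. Contraception concerns pregnancy, follow-up was chosen for safety monitoring and for exploring duration of response, and the five-half-life rule is an entry washout for other biologics. That is fair. They show that longer periods already exist in the protocol, not that 12 weeks is the correct vaccine interval.

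A third reply is that the clearance sentence concerns vaccine failure, that is, antibody levels too low to protect, not infection from the vaccine. That is also correct. The infection risk is inferred from the separate immunosuppression statement, which is conditional on full occupancy.

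A reader might infer that CD40 stays blocked over the whole 56 days from Day 169 to Day 225. The documents do not support that: the stated aim ends with the treatment period, and Section 3.2 expects rapid elimination once saturation is incomplete.

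**Conclusion.** The point holds as an internal mismatch in Cohort 2: the minimum ban can end on Day 169, when the regimen is still designed to keep CD40 saturated. It rests on the stated design aim, full dosing to Day 141, and the absence of a later limit in the visible text.

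The size is small and may be nil. About 30 patients are randomized to Cohort 2, and former placebo patients also receive CFZ533, so 30 is the ceiling. About 24 are expected to complete the first 12 weeks, so fewer than 30 are likely to reach the Day 141 dose. Patients whose vaccinations are not up to date are excluded, and the number who would want a live vaccine is not given.

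Two wider readings should be resisted. The documents do not show that four weeks is unsafe; that depends on PK and receptor-occupancy data not available here. Nor does the argument carry equally to the other cohorts. For Cohort 1, the visible text ties full saturation to the two-week interval at the start. For Cohort 3, Section 3.2 foresees a saturated phase after the last dose but gives no length. This is a cheap safety improvement, not a demonstrated harm.

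**What to change.** Change the live-vaccination row of Table 5-3 only: no live vaccine until at least 12 weeks after the last dose, or longer if the sponsor's PK and receptor-occupancy data show later clearance. Align the sentence on live attenuated agents in Section 3.6.2 with the same period, and tell the patient the date no later than the last visit. In Cohorts 1 and 2 the last dosing visit is the better moment, because the patient needs the date before Day 169. Leave the other rows as they are; a patient with a flare may need those treatments, and Section 5.5.8 already handles immunosuppressives case by case.

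The cost is one table row, one sentence and one line of patient information. At 12 weeks no visit is added: the date is Day 225 in Cohorts 1 and 2, the end-of-study visit. In Cohort 3 it is Day 169, after the last visit (Day 141) but before the 30-day safety contact (141 + 30 = Day 171). A patient who wants a live vaccine waits at least 8 weeks longer. If the sponsor's data call for more than 12 weeks, the restriction runs past the last visit (for example to Day 246 in Cohort 2 under the assumed 21-day half-life), and the patient would then have to rely on the date given.

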5.5.10 Discontinuation of study treatment

Study “Stopping rules”

The following stopping rules, based on potential toxicities, will serve as the basis for placing the study on hold. Although the stopping criteria do not incorporate an absolute requirement for causality, the potential relationship between an adverse event and CFZ533 will be evaluated carefully on a case-by-case basis between the Sponsor and the Investigator. Following a review of the adverse event(s), a decision to permanently discontinue enrollment or re-initiate dosing will be made jointly by the Investigator and Sponsor.

As a guidance, dose limiting toxicities (DLTs) will be assessed according to the standardized toxicity grading scale, the NCI Common Toxicity Criteria for Adverse Events (NCI-CTCAE/v4.03, Reference <http://evs.nci.nih.gov/ftp1/CTCAE/About.html>).

- Any study treatment related death,
1. Two (2) or more subjects presenting with a serious adverse event that is related to the study treatment,
 2. One (1) subject presenting with study treatment related cytokine release syndrome,
 3. One (1) subject presenting with a study treatment related thromboembolic event that is at least of moderate severity,
 4. More than one (1) allergic reaction of Grade 3 severity of the NCI-CTCAE/v4.03 Criteria within the first 5 treated subjects or an incidence of >20% thereafter,
 5. Any treatment-related, Grade 3 or higher event of the NCI-CTCAE/v4.03 Criteria considered drug related by the Investigator with the following exceptions:
 1. Events not requiring treatment, and diagnostic procedures involving elective or non-urgent hospital admission,
 2. Disease Specific Events that are due to the patients underlying pSS diagnosis,
 3. AEs/SAEs unrelated to the experimental compound as determined by the Investigator or Novartis

6. Two (2) or more subjects presenting with:
 4. Progressive renal insufficiency or acute kidney injury defined as a Grade 2 increase in serum creatinine (1.5 X ULN) in the setting of euvoemia at any time during the study,
 5. Emergent hypogammaglobulinemia defined as a reduction in total serum IgG or IgM concentration by 50% or more from baseline,
 6. Severe systemic infection or opportunistic infection that requires treatment, e.g., sepsis, urosepsis, mycoses, pneumonia.
7. Clinically significant (according to the Investigator) and study drug-related, persisting changes from baseline in vital signs, electrocardiograms, or relevant, persistent changes in laboratory parameters, which are not consistent with existing co-morbidities, in more than one (1) subject within the first 5 treated subjects or an incidence of >20% thereafter.
8. Other clinically significant changes or effects in the opinion of the Investigator or Sponsor that are deemed unsafe to continue dosing.

In addition, all blinded safety data, including disease specific events, will be evaluated by the Sponsor and Investigator continuously and at scheduled meetings. The study may be put on hold pending further data analysis, and the decision to adjust the dose or modify the medication if the following criteria occur:

- The principal investigator or the Sponsor considers that the number and/or severity of AEs justify discontinuation of the study.
- Other clinically significant changes or effects in the opinion of the Investigator or Sponsor that are deemed unsafe to continue dosing.

Individual subject withdrawal

Subjects may voluntarily discontinue the study for any reason at any time.

The Investigator should discontinue study treatment for a given subject if, on balance, he/she believes that continuation would be detrimental to the subject's well-being.

Study treatment **must** be discontinued under the following circumstances:

- Subject withdraws consent,
- Pregnancy,
- CTCAE Grade 3-4 allergic reaction,
- Major worsening of primary Sjögren's syndrome as judged by the Investigator (e.g., severe CNS or renal complications, or increase from baseline in ESSDAI of at least 7 points after more than 8 weeks of treatment (as a guidance),
- Acute, severe infection as judged by the investigator,
- Significant changes in standard coagulation test, such as prothrombin time (PT) or activated partial thromboplastin time (aPTT), suggesting an increased risk for hypercoagulability or any sign or symptom of a thromboembolic event.

Discontinuation of study treatment will be at the discretion of the Investigator, under the following circumstances:

- Any other protocol deviation that results in a significant risk to the subject's safety

The appropriate personnel from the site and Novartis will assess whether study treatment should be discontinued for any subject whose treatment code has been broken inadvertently for any reason.

Subjects who discontinue study treatment should NOT be considered withdrawn from the study UNLESS they withdraw their consent (see [Section 5.5.11](#)). They should return for the assessments indicated by an asterisk (*) in the assessment table. If they fail to return for these assessments for unknown reasons, every effort should be made to contact them as specified in [Section 5.5.12](#).

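### Stopping rule 4 counts only Grade 3 allergic reactions, so read literally a Grade 4 reaction does not count towards the study hold

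*Protocol*

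**What the plan says.** Protocol 5.5.10 lists the events that place the whole study on hold. Rule 4 deals with allergic reactions. Its trigger is "More than one (1) allergic reaction of Grade 3 severity of the NCI-CTCAE/v4.03 Criteria within the first 5 treated subjects", or an incidence above 20% thereafter. It names no relatedness condition, which fits the preamble, where "the stopping criteria do not incorporate an absolute requirement for causality".

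Other rules in the section set their severity level differently:

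- Rule 3: "One (1) subject presenting with a study treatment related thromboembolic event that is at least of moderate severity".
- Rule 5: "Any treatment-related, Grade 3 or higher event of the NCI-CTCAE/v4.03 Criteria considered drug related by the Investigator with the following exceptions".
- Individual subject withdrawal, where treatment must stop: "CTCAE Grade 3-4 allergic reaction".

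Several other provisions can reach a severe allergic reaction:

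- The death rule: "Any study treatment related death".
- Rule 1: "Two (2) or more subjects presenting with a serious adverse event that is related to the study treatment".
- Rule 8: "Other clinically significant changes or effects in the opinion of the Investigator or Sponsor that are deemed unsafe to continue dosing".
- A separate discretionary hold in the same section, based on the number or severity of adverse events.

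No visible text in the protocol or the SAP extends rule 4 to Grade 4.

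**The concern.** A rule that counts reactions at exactly one grade leaves out the worse grade. The closest comparison is the individual withdrawal criterion, which covers the same event on the same scale in the same section and names both Grade 3 and Grade 4. A Grade 4 reaction therefore must end that subject's treatment, yet on the wording it does not move the study-level count for the same event. The protocol gives no reason for the difference. Someone comparing rule 4 with rule 5 could take it as deliberate.

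Rule 4 is the only study-level rule that names allergic reactions and counts them without asking about causality. Such a count has a purpose here. In Cohorts 1 and 2 the investigator judges causality blinded (5.4), there is no data monitoring committee (8.4), and 5.5.6 foresees acute, severe reactions to parenteral antibodies. What is at stake is a hold by count, rather than by opinion, when a cluster judged unrelated includes Grade 4 reactions.

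**Working it through.** The plan states no operating characteristics for rule 4, so there is no figure to reproduce. The check has three steps.

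**1. Which reactions depend on rule 4 alone.** Rule 5 holds the study after a single Grade 3 or higher event, but the investigator must consider it drug related. Its exceptions remove events not requiring treatment and events that the investigator or the sponsor determines to be unrelated. Rule 1 and the death rule also require relatedness. Rule 8 and the discretionary hold need no relatedness but rest on opinion. For non-fatal reactions judged unrelated, rule 4 is the only rule left that acts on a count. The rest of the working assumes this situation, with at most one reaction per subject. That is reasonable, because a Grade 3 or 4 reaction ends the subject's treatment.

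**2. First five treated subjects.** A hold needs a count above 1. The grade mixes are assumed.

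| Reactions | Count as written | Hold? | Count with 'Grade 3 or higher' | Hold? |
|---|---|---|---|---|
| Two Grade 3 | 2 | yes | 2 | yes |
| One Grade 3, one Grade 4 | 1 | no | 2 | yes |
| Two Grade 4 | 0 | no | 2 | yes |

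To show how often this could matter, let p be the per-subject probability of a counted reaction. The chance of at least two in five subjects is 1 − (1 − p)^5 − 5p(1 − p)^4. As written, p is the Grade 3 rate. With 'or higher', p is the sum of the two rates. All rates are assumed.

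| Grade 3 rate | Grade 4 rate | As written | With 'or higher' |
|---|---|---|---|
| 5% | 5% | 2.3% (p = 0.05) | 8.1% (p = 0.10) |
| 10% | 10% | 8.1% (p = 0.10) | 26.3% (p = 0.20) |
| 20% | 10% | 26.3% (p = 0.20) | 47.2% (p = 0.30) |

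For comparison, at 10% and 10% the chance of at least one Grade 3 or higher reaction in five subjects is 1 − 0.8^5 = 67.2%. Rule 5 would act on that one reaction if it were judged related and no exception applied.

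**3. After the first five.** The incidence is taken over all subjects treated so far, with at most one reaction among the first five. The smallest count above 20% of n is floor(0.2n) + 1. Planned sizes are from Protocol section 4: 12, 30 and 24 for Cohorts 1, 2 and 3.

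| Treated | 0.2n | Count needed | Just above | Just below |
|---|---|---|---|---|
| 24 (Cohort 3) | 4.8 | 5 | 5/24 = 20.8% | 4/24 = 16.7% |
| 42 (12 + 30) | 8.4 | 9 | 9/42 = 21.4% | 8/42 = 19.0% |
| 66 (12 + 30 + 24) | 13.2 | 14 | 14/66 = 21.2% | 13/66 = 19.7% |

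At 24 treated, four Grade 3 plus one Grade 4 give 4/24 as written (no hold) and 5/24 with 'or higher' (hold).

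The protocol does not say whether the first five subjects and the 20% limit apply per cohort or to the whole study. Section 3.1 sends all new patients after Amendment 6 to Cohort 3. If the rule is study-wide, only the 20% clause is still live there.

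**The case against.** The strongest reply is that the gap has almost no consequence. For related reactions rule 5 is stricter than rule 4, since one event is enough. A life-threatening reaction is also an SAE under 7.1, so two related ones meet rule 1. What remains is a cluster of severe allergic reactions, at least one of them Grade 4, all judged unrelated to a parenteral antibody, with nobody using rule 8 or the discretionary hold. Every SAE reaches the sponsor within 24 hours whatever its cause (7.2), and joint safety reviews are provided for (7.5). CTCAE grading is introduced as guidance, and most readers would count a Grade 4 reaction anyway. All the grade mixes and rates above are assumed.

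Most of this stands, and it limits the weight of the point. It would be wrong to say that Grade 4 allergic reactions cannot stop this study, and rules 1 and 5 are also count triggers that reach them. But those rules and the death rule depend on relatedness, and the others depend on opinion. None replaces a count that is independent of causality. That readers would probably correct the rule for themselves is no reason to leave it giving the wrong count when followed as written.

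**Conclusion.** The point holds. As written, rule 4 leaves Grade 4 allergic reactions out of its count, and nothing visible elsewhere corrects this. It reads as a drafting slip, not a considered choice. The difference is between a hold and no hold for mixes such as one Grade 3 plus one Grade 4 among the first five subjects, or four plus one among 24. It arises only for reactions that no other rule holds, mainly those judged unrelated. In practice the effect is probably small, because a discretionary hold would be likely to come first, particularly under the 20% clause. Some hypersensitivity text in 3.6.2 and 5.5.6 is redacted, and 3.6.2 refers to the Investigator's Brochure for risk mitigation, so the remaining risk cannot be fully judged. The change is optional but worth making.

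**What to change.** In Protocol 5.5.10, rule 4, insert 'or higher' after 'Grade 3', so that the rule counts allergic reactions of Grade 3 or higher severity. Leave the count in the first five subjects, the 20% limit and all other rules unchanged. This brings rule 4 into line with rule 5 and with the individual withdrawal criterion.

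The cost is two words in the next amendment, with no new data, visits or analyses. The only downside is possibly a few more temporary holds, which the joint review by investigator and sponsor can lift.
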